## **7.5 Capecitabine**

Description: Capecitabine (Xeloda) is a fluoropyrimidine carbamate with antineoplastic activity. It is an orally administered systemic prodrug of 5'-deoxy-5-fluorouridine (5'-DFUR) that is converted to 5-fluorouracil.

Form: Capecitabine is supplied as a biconvex, oblong film-coat tablets for oral administration. Each light-peach colored tablet contains 150 mg capecitabine, and each peach colored tablet contains 500 mg capecitabine.

Storage and Stability: Store at 25° C (77° F); excursions permitted to 15° to 30° C (59° to 86° F), keep bottles or storage devices tightly closed.

Compatibility: Capecitabine and some of its metabolites are converted principally by liver enzymes (carboxylesterase and cytidine deaminase and TP in tumor tissues). At present, it is unknown whether this metabolism is likely to be influenced by other treatments or alcohol, which either induce or inhibit certain liver enzymes.

Allopurinol: Oxypurinol, a metabolite of allopurinol, can potentially interfere with 5-FU anabolism via orotate phosphoribosyltransferase. Although this was originally used as a strategy to protect normal tissues from 5-FU-associated toxicity, further laboratory studies suggested possible antagonism of the anticancer activity of 5-FU in some tumor models. If a patient is receiving allopurinol, the need for taking this medicine should be ascertained. If possible, allopurinol should be discontinued prior to starting on this regimen, and another agent substituted for it.

Sorivudine and Brivudine: A metabolite of the above two investigational antiviral agents, 5-bromovinyluracil, is a potent inhibitor of dihydropyrimidine dehydrogenase, the enzyme that catabolizes 5-FU. Patients should not receive concurrent therapy with either of these antiviral agents while receiving capecitabine. If a patient has received prior sorivudine or brivudine, then at least four weeks must elapse before the patient receives capecitabine therapy

**Anticoagulants:** See Warnings and Precautions Section 6.9 In a drug interaction study with single dose warfarin administration, there was a significant increase in the mean AUC of S-warfarin. The maximum observed INR value increased by 91%. This interaction is probably due to an inhibition of cytochrome P450 2C9 by capecitabine and/or its metabolites.

**Phenytoin:** Increased phenytoin plasma concentrations have been reported during concomitant use of Xeloda® with phenytoin, suggesting a potential interaction. Patients taking phenytoin concomitantly with Xeloda® should be regularly monitored for increased phenytoin plasma concentrations and associated clinical symptoms.

**Laxatives:** The use of drugs with laxative properties should be avoided.

#### Warnings and Precautions:

**Renal Insufficiency:** Patients with moderate renal impairment as measured by serum creatinine ( $> 1.3$ ) at baseline require dose reduction (see section 4.1.3). Patients with mild and moderate renal impairment at baseline should be carefully monitored for adverse events. Prompt interruption of therapy with subsequent dose adjustments will be made if a patient develops a grade 2 to 4 adverse event. Capecitabine is contraindicated in patients with a calculated creatinine clearance of  $< 30$  ml/min. Creatinine level will be checked and creatinine clearance calculated on Study Day 8 for all subjects to ensure safety of continued administration of capecitabine.

**Pregnancy/Nursing:** Capecitabine may cause fetal harm when given to a pregnant woman. If the drug is used during pregnancy, or if the patient becomes pregnant while receiving this drug, the patient should be apprised of the potential hazard to the fetus. Women of childbearing potential should be advised to avoid becoming pregnant while receiving treatment with capecitabine. Because of the potential for serious adverse reactions in nursing infants from capecitabine, the patient will be instructed that nursing must be discontinued when receiving capecitabine therapy.

**Coagulopathy:** Patients receiving concomitant capecitabine and oral coumarin-derivative anticoagulant therapy should have their anticoagulant response (INR or prothrombin time) monitored frequently in order to adjust the anticoagulant dose accordingly. A clinically important Capecitabine-Warfarin drug interaction was demonstrated in a clinical pharmacology trial. Altered coagulation parameters and/or bleeding, including death, have been reported in patients taking capecitabine concomitantly with coumarin-derivative anticoagulants such as

warfarin and phenprocoumon. Postmarketing reports have shown clinically significant increases in prothrombin time (PT) and INR in patients who were stabilized on anticoagulants at the time capecitabine was introduced. These events occurred within several days and up to several months after initiating capecitabine therapy and, in a few cases, within one month after stopping capecitabine. These events occurred in patients with and without liver metastases. Age greater than 60 and a diagnosis of cancer independently predispose patients to an increased risk of coagulopathy.

**Cardiotoxicity:** The cardiotoxicity observed with capecitabine includes myocardial infarction/ischemia, angina, dysrhythmias, cardiac arrest, cardiac failure, sudden death, electrocardiographic changes, and cardiomyopathy. These adverse events may be more common in patients with a prior history of coronary artery disease.

This treatment is foreseen as a self-administered out-patient treatment, and in certain circumstances adverse events that could occur, such as diarrhea, or hand-foot syndrome can rapidly become serious. In the case where a patient experiences any toxicity between scheduled visits, the patient will be instructed to contact the clinic as soon as possible, for further directions, discontinuation of study medication, and/or treatment.

**Handling:** Qualified personnel, familiar with procedures that minimize undue exposure to themselves and the environment, should undertake the preparation, handling, and safe disposal of capecitabine in a self-contained and protective environment.

**Availability:** Capecitabine is commercially available and will not be provided free of charge by the study. It is expected that the study participants or their insurers will be responsible for the cost of Capecitabine.

#### *Preparation*

N/A- Capecitabine comes in tablet formulation

#### *Administration*

Tablets should be swallowed with water 30 minutes after the end of a meal (breakfast and dinner). If necessary, tablets may be crushed.

### *Ordering*

Capecitabine will be prescribed by the treating medical oncologist; prescriptions will be filled by the study participants at their pharmacy of choice.

### *Accountability*

N/A drug is not study supplied.

### *Destruction and Return*

N/A drug is not study supplied.

## **7.6 Losartan**

### *Supply*

Losartan will be study supplied for this trial. Study participants will receive Losartan free of charge.

### *Availability*

Losartan will be study supplied in 25mg and 50mg tablets. Study participants will be asked to return unused pills at each follow up visit. Pill counts will be conducted to maintain drug accountability. Once counted, unused pills will be returned to the Research Pharmacy for destruction.

### *Onset and Duration*

Hypertension, oral: 6 hours (Ohtawa et al, 1993a; Weber, 1992). In some studies, the maximal effect occurred in 3 to 6 weeks (Prod Info Cozaar(R), 2000).

Once-daily oral doses of LOSARTAN 50 to 150 mg have produced significant antihypertensive effects for 24 hours (Tsunoda et al, 1993a; Weber, 1992). This was not achieved with lower doses (10 or 25 mg), which were similar in efficacy to placebo (Weber, 1992). Peak and trough responses (adjusted) following 8 weeks treatment with 3 dose levels

are summarized, showing a lack of clearly distinguishable differences (Elliott, 1998):

Losartan dose	Change in Blood Pressure mmHg	
	Peak	Trough
50 mg	13.5/7.2	9.5/4.8
100 mg	11.9/5.7	5.9/4.4
150 mg	11.7/7.5	6.8/4.1

#### *Metabolism*

Liver, 14% : LOSARTAN is extensively metabolized by cytochrome P450-2C9 and -3A4.

Metabolites include 5-carboxylic acid (E-3174), (active). Animal studies have suggested that E-3174 is up to 40 times as potent as LOSARTAN in angiotensin II blocking activity.

Although LOSARTAN is also pharmacologically active, E-3174 appears responsible for the prolonged hypotensive effects observed after oral LOSARTAN administration.

#### *Storage and Stability*

Protect tablets from light in a tightly closed container stored at controlled room temperature of 15 to 30 degrees Celsius (59 to 86 degrees Fahrenheit) (Prod Info Cozaar(R), 2002). Shelf life stability is 3 years from the date of packaging although the commercially available products carry 18 month expiration dating (Tech Info Cozaar(R), 1995).

#### *Administration*

Patients will self-administer Losartan tablets at 25mg PO QD or 50 mg PO QD. Blood pressure monitoring will occur in the clinic, and dose modification based on serial low blood pressure will be per toxicity guidelines at the discretion of the treating physician (section 6).

#### ***Drug Interactions (major)***

##### **Lithium**

Interaction Effect: an increased risk of lithium toxicity (weakness, tremor, excessive thirst, confusion) There is evidence that angiotensin II receptor antagonists may substantially increase steady-state plasma lithium levels, sometimes resulting in lithium toxicity. Patients prescribed lithium and losartan should be closely monitored for the development of lithium toxicity. Plasma lithium levels should also be followed.

### **Naproxen and other NSAIDS**

Interaction Effect: decreased antihypertensive effects and an increased risk of renal impairment. Reports indicate that the concomitant use of an NSAID with an angiotensin II receptor blocker (ARB) may decrease the antihypertensive effect of the ARB (Prod Info CELEBREX(R) oral capsules. Additionally, renal deterioration and acute renal failure may result , especially in volume-depleted patients. Renal function should be monitored periodically in patients receiving ARB and NSAID therapy

## **8 OPTIONAL CORRELATIVE STUDIES**

### **8.1 Laboratory Correlative Studies**

#### **8.1.1 Circulating Biomarkers: Anti-fibrotic effects**

In pre-clinical and clinical studies circulating levels of collagen or profibrogenic molecules are used as surrogate biomarkers of the efficacy of RAS inhibition or other anti-fibrotic agents. We will determine how losartan affects plasma levels of ATII, collagen I and IV, and downstream mediators of ATII signaling [transforming growth factor  $\beta$ 1 (TGF $\beta$ 1), connective tissue growth factor (CTGF), thrombospondin-1 (TSP1), osteopontin] and profibrogenic cytokines [stromal derived factor-1 $\alpha$  (SDF-1 $\alpha$ ), interleukin (IL)-1 $\beta$ , IL-4, IL-10, and IL-13]. Granulocytes are a major source of TGF $\beta$  in PDAC. Therefore, we will measure how losartan affects the number of granulocytes in peripheral blood using flow cytometry and CBC. Because losartan modulates the levels of vascular endothelial growth factor (VEGF) and angiogenesis, we will also determine the circulating levels of angiogenic molecules. The changes in plasma biomarkers will be correlated with therapeutic response, outcome, tumor uptake of  $^{18}\text{F}$ -5FU and microvascular imaging parameters (see section 8.1.2).

Blood will be drawn by venipuncture, and the first 7-10 ml blood will be excluded or used for other analysis. The following 8 ml will be collected in an EDTA tube. The EDTA tube with the blood sample will be shipped in wet ice within 2 hours of drawing for further processing at Steele Laboratory at MGH.

Blood samples will be collected on Day 1, 8, 29 and 92. The day 29 and 92 blood draws may be completed +/- 3 days from their scheduled date. Blood can be drawn for this study at any time most convenient for the study participant.

Based on findings from preliminary studies, we propose here to evaluate the changes in blood circulating SDF1 $\alpha$  and circulating myeloid cells throughout the treatment course to explore potential associations between the changes in these biomarkers and resistance to treatment. In exploratory studies, we will evaluate several other cytokines using multiplex protein array (Meso-Scale Discovery, Inc.). We will use ELISA kits to measure plasma levels of collagen I (Cosmo Bio Co.), collagen IV (Echelon BioSciences Inc), human cross-linked carboxy-terminal telopeptide of collagen I (Cusabio), ATII (Assaypro), CTGF, TGF $\beta$ 1, TSP-1, osteopontin, soluble vascular endothelial growth factor receptor 2, angiopoietin 2 and SDF-1 $\alpha$  (R&D Systems). Multiplex ELISA plates (Meso-Scale Discovery) will be used to analyze plasma levels of VEGF, placenta growth factor (PIGF), soluble VEGF receptor 1 (sVEGFR1), basic fibroblast growth factor (bFGF), VEGF-C, VEGF-D, sTie2, tumor necrosis factor alpha (TNF- $\alpha$ ), and IL-1 $\beta$ , IL-4, IL-10, and IL-13. Granulocytes (CD11b+Ly6G+CD115-) will be enumerated in fresh samples using a standard flow cytometry protocol. In addition, we will analyze the correlation between plasma SDF1 $\alpha$  and circulating myeloid cells with multiple measures of outcome (ORR, TTP, OS) in pancreatic cancer patients after losartan treatment.

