#### **8.1.2.1 Experimental Design**

Blood for correlative research may be drawn via port-a-cath or peripheral venipuncture. The blood draw site should remain consistent across all correlative lab timepoints for each patient throughout their participation in the trial. The first 7-10 ml blood will be excluded or used for other analyses. The following 8 ml will be collected in an EDTA tube. The EDTA tube with the blood sample will be shipped in wet ice within 2 hours of drawing for further processing at

Steele Laboratory at MGH. We will analyze the correlation between plasma cytokines and circulating myeloid cells with multiple measures of outcome (ORR, TTP, OS) in patients with borderline resectable pancreatic cancer before, during, and after treatment.

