### 14.3 Analysis of Secondary Endpoints

- 14.3.1 **Progression-free survival:** All patients who start induction chemotherapy will be analyzed based on the definition in Section 10.1.2. The progression-free survival duration of patients who are alive and progression will be censored at their date of last follow-up. The Kaplan-Meier method will be used to estimate progression-free survival with 90% confidence intervals constructed by Greenwood's formula.
- 14.3.2 **Overall survival:** Overall survival will be defined as the duration between the start date of protocol therapy and death. The survival time of patients who are not known to have died will be censored at the date they are last known to be alive. The Kaplan-Meier method will be used to estimate overall survival estimation with 90% confidence intervals constructed by Greenwood's formula.
- 14.3.3 **Toxicities:** All patients who begin induction chemotherapy will be included in the toxicity profile of Losartan combined with induction FOLFIRINOX. Summaries of toxicities will include the frequency and proportion of patients experiencing each toxicity, as well as summaries by toxicity category and toxicity grade. We shall report separately the additional treatment-related toxicity following radiation in patients who do not have progressive disease at the restaging interval after induction chemotherapy.
- 14.3.4 **Downstaging:** A fraction of patients may proceed to surgical resection following the conclusion of protocol therapy if the tumor shrinkage were sufficient to be considered resectable. The rate of downstaging to surgical resection will be determined as the proportion of initially unresectable patients who eventually undergo pancreaticoduodenectomy or distal pancreatectomy. The pathologic downstaging rate will be calculated as the proportion of resected patients with the primary tumor and nodes downstaged based on final pathology of the surgical specimen.
- 14.3.5 **Correlation of biomarkers with outcome:** Correlative studies will be conducted to characterize circulating collagen and angiogenesis biomarkers (8.1.1), as well as somatic genetic mutations characterized by the SNaPshot platform (8.1.2). Due to the modest patient numbers, analysis will be limited generally to two-group comparisons of each

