biomarker. Continuous values will be dichotomized at the median or a biologically meaningful threshold. The logrank test will be used to assess differences in progression-free survival and overall survival by biomarker status if at least 5 failure events have been observed within each subgroup. The correlative analysis will be purely exploratory due to the limited numbers expected per biomarker subgroup. In particular, analysis will be descriptive when the frequency of a genetic mutation is low.

14.3.6 ***Patient-reported outcomes***: We will use descriptive statistics to describe QOL (EORTC QLQ-C30), symptom burden (ESAS-r) and mood (HADS) for the entire study cohort. Mean values and standard deviations will be used to describe QOL and symptom burden (T-test or Wilcoxon as appropriate). We will score the HADS subscales for depressive and anxiety symptoms categorically, using a cut-off of >7 to describe the proportion of patients with these symptoms. We will use Chi-square or Fisher's Exact Test, as appropriate, to analyze the categorical variables.

14.3.7 ***Health care utilization***: We will use descriptive statistics to describe hospitalizations, ICU stays, ED visits and palliative care use for the entire study cohort. Mean values and standard deviations will be used to describe continuous variables (T-test and Wilcoxon rank sum, as appropriate). We will use Chi-square or Fisher's Exact Test, as appropriate, to analyze the categorical variables.

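### The flow gate for granulocytes in patients' blood uses Ly6G, a mouse marker: that count cannot be obtained as written, the CBC count remains, and circulating myeloid cells have no stated marker definition

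*Combined protocol and SAP*

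**What the plan says.** Section 8.1.1 gives the aim and names two methods: "Therefore, we will measure how losartan affects the number of granulocytes in peripheral blood using flow cytometry and CBC". Later in the same section the flow definition follows: "Granulocytes (CD11b+Ly6G+CD115-) will be enumerated in fresh samples using a standard flow cytometry protocol".

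The blood is human. The same section plans to correlate plasma SDF1α and "circulating myeloid cells with multiple measures of outcome (ORR, TTP, OS) in pancreatic cancer patients after losartan treatment". Section 8.1.2.1 repeats the plan for circulating myeloid cells with the same three outcomes. Section 8.1.1 also intends to follow these cells over the treatment course and to look for links with resistance. Neither section gives markers for them.

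Section 8 is headed "OPTIONAL CORRELATIVE STUDIES", and a note to the study calendar says that these draws are optional. Section 14.3.5 says of the analysis: "The correlative analysis will be purely exploratory due to the limited numbers expected per biomarker subgroup".

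**The concern.** The gate is specific, so this is not a matter of missing detail. It names three conditions, and one of them relies on an antigen of another species. A laboratory that followed the text would record a granulocyte count close to zero, or one made up of background staining, and nothing in the protocol would flag that value as invalid.

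Two things are at stake. One is the flow arm of the granulocyte measurement. The cells are counted in fresh samples, so stored plasma cannot supply the count later. The other is interpretability of the planned correlation with outcome. Because the granulocyte gate is the only cell-marker definition in the section, an analyst might adopt it for circulating myeloid cells by default, and would then carry an invalid variable into those comparisons.

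**Working it through.** No figure in the plan depends on this gate, so there is nothing to reproduce. The check is a reading of the relevant sections together.

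1. **Species of the sample.** Sections 8.1.1 and 8.1.2.1 describe EDTA blood drawn from trial participants. No animal sample is collected in this trial.

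2. **What the gate requires.** A cell is counted only if it is CD11b positive, and Ly6G positive, and CD115 negative. The conditions are joint. If no human cell carries Ly6G, the joint set is empty whatever the other two markers show. Any events left in it are non-specific staining.

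3. **Source of the species fact.** The documents do not state the species of Ly6G. That it is a mouse antigen is basic assay nomenclature. It is taken here as an assumption and not as a figure from an outside source.

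4. **Is another definition given?** No human granulocyte panel appears anywhere in the protocol.

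5. **Does a second route to the count exist?** Yes. Section 8.1.1 names the CBC beside flow cytometry. The section 9 calendar schedules CBC with differential at baseline, weekly in cycle 1, every other week in later cycles, at restaging, weekly during radiation and in follow-up.

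6. **Does the CBC line up with the research draws?** Not always. Section 8.1.1 sets research draws on Days 1, 8, 29 and 92. With 14-day cycles:
   - Cycle 3 Day 1 is 2 × 14 + 1 = Day 29, a treatment day.
   - Cycle 7 Day 1 is 6 × 14 + 1 = Day 85, so Day 92 is cycle 7 Day 8.
   - Cycle 8 Day 1 is 7 × 14 + 1 = Day 99.

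   After cycle 1 the CBC is every other week. On the nominal schedule Day 92 falls 7 days after one CBC and 7 days before the next, so no same-day CBC is scheduled there.

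7. **Is the granulocyte gate the definition of circulating myeloid cells?** The text never says so. The aim attached to granulocytes is to see how losartan affects their number. The correlation with outcome is attached to circulating myeloid cells, a broader term that would ordinarily include monocytes. That term has no markers of its own.

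8. **What else depends on it?** The primary endpoint in section 14 is R0 resection on final pathology, judged by at least 9 of 50 patients. Neither the rule nor its stated operating characteristics use the biomarker data. Objective 1.3.8 names TGF-β1 downregulation markers and collagen I. Section 14.3.5 names collagen and angiogenesis biomarkers and the SNaPshot mutations. Neither mentions granulocytes or myeloid cells.

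**The case against.** The strongest reply is that this is a copied label with no effect on data. The text refers to a standard flow protocol, and the laboratory may have used human antibodies throughout. The CBC gives the granulocyte number in any case, and the whole section is optional and exploratory. Much of this stands. The documents cannot show which reagents were used, and the low stakes are real. What remains is that the written definition cannot be carried out in human blood, and that relying on the CBC alone gives up one of two planned measurements together with any cell subset that a differential cannot resolve.

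A reader might also draw stronger conclusions that the documents do not support:

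- *That granulocytes cannot be measured, or that the myeloid-cell endpoint is lost altogether.* The CBC is a named second method and is scheduled repeatedly. Circulating myeloid cells are undefined, which differs from being defined by a gate that fails.
- *That every flow value is lost and the last 18 of 50 patients can be rescued.* This assumes that the mouse reagent was actually used and that the undated accrual statement in section 14 is current. Because the draws are optional, 50 is only a ceiling.
- *That these are the trial's lead biomarkers.* Section 8.1.1 does place SDF1α and myeloid cells ahead of the other cytokines, but the listed objective and the analysis section do not name myeloid cells.
- *That the gate was carried over from the mouse work in section 2.2.3.* The account there of losartan in mouse tumours deals with collagen, drug penetration and tumour growth. It says nothing about granulocytes or flow cytometry.

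**Conclusion.** The specification is wrong as written. The flow-based granulocyte count cannot be obtained with the stated gate in patients' blood. The CBC-based count remains, and circulating myeloid cells have no stated marker definition.

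The severity is low. The work is optional and purely exploratory, no sample size or error rate is attached to it, and the primary endpoint and safety analyses are unaffected. The number of affected measurements cannot be given from the documents: it runs from none, if human antibodies were used, to all flow granulocyte counts taken, if the stated gate was followed.

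The conclusion rests on one assumption from outside the text, that Ly6G is a mouse antigen and not a usable marker on human granulocytes. It does not depend on what the laboratory actually did.

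**What to change.** 1. In section 8.1.1, replace the gate with the laboratory's own validated human granulocyte definition, for example one based on CD15 and CD66b. The choice of panel belongs to the laboratory.
2. In sections 8.1.1 and 8.1.2.1, define circulating myeloid cells separately. Do not reuse the granulocyte gate, since a granulocyte-only definition would leave out monocytes and narrow the measure.
3. For samples already run, confirm from laboratory records which antibodies were used. If a valid human panel was used, only the protocol text needs correcting.
4. If the stated gate was used, do not analyse those flow values. Report the granulocyte count from the nearest available CBC differential, with the gap in days, because no same-day CBC is scheduled at Day 92.

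The cost is a short change of wording in the protocol or laboratory manual and a check of reagent records. If the mouse reagent was in use, the antibodies must be changed for remaining samples, and the effort depends on the panel chosen. The correction itself calls for no additional visit.
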